## STUDY DEFINITIONS

Abbreviations	Definition
AE	Adverse Event
BSL	Biosafety Level
CDC	Centers for Disease Control and Prevention
CI	Confidence Interval
COVID-19	Coronavirus Disease 2019
EUA	Emergency Use Authorization
FDA	Food and Drug Administration
FP	False Positive
FN	False Negative
GCP	Good Clinical Practice
GLP	Good Laboratory Practice
ICU	Intensive Care Unit
ID	Identification
IUO	Investigational Use Only
IFU	Instructions for Use
IRB	Institutional Review Board
LFA	Lateral-Flow Immunoassay
LoD	Limit of Detection
LOS	Length of Stay
MERS	Middle East Respiratory Syndrome
NPA	Negative Percent Agreement
PHEIC	Public Health Emergency of International Concern
PHI	Protected Health Information
PI	Principle Investigator
POC	Point of Care
PPA	Positive Percent Agreement
RNA	Ribonucleic Acid
RT-PCR	Reverse Transcription Polymerase Chain Reaction
SARS-CoV	Severe Acute Respiratory Syndrome Coronavirus
sFTP	Secure File Transfer Protocol
TP	True Positive
TN	True Negative
UADE	Unanticipated Adverse Device Effect
US	United States
WHO	World Health Organization

## RESPONSIBILITIES

This section details the responsibilities of the PI, the Sponsor, and the study monitors.

Role	Responsibilities

Investigator	
 
• Obtain IRB approval for protocol prior to study initiation, if needed.
 
• Conduct study in accordance with signed Statement of Investigator, study protocol, GCP, GLP, other applicable country specific regulations.
 
• Submit proposed protocol amendments or deviations to IRB and sponsor and obtain approval.
 
• Submit progress reports, final reports, and special reports to IRB, when applicable.
 
• Supervise the use of the IUO device.
 
• Permit country specific regulatory agency and Sponsor's Clinical Affairs Staff to inspect facilities and records or delinked records as applicable.
 
• Refrain from promoting investigational materials.
 
• Retain study records according to Phase Diagnostics and country specific regulations.
 

Sponsor (Phase Diagnostic Inc.)	
 
• Provide approved Study Protocol.
 
• Verify investigators are qualified by training and experience.
 
• Verify IRB approval of protocol has been obtained prior to study initiation.
 
• Verify Clinical Trial Agreement has been fully executed prior to study initiation.
 
• Select qualified monitors.
 
 
Provide all testing materials needed for the study. Provide Study Protocol, testing instructions and selection criteria for testing sites, operators and participants. Approve selected testing sites and operators. Data review and analysis.
 
 
• Assign a Monitor to conduct periodic monitoring visits which include, but are not limited to: 
 
○ Audit case report forms against source documents as appropriate and verify accuracy and completeness.
 
○ Document and investigate missing data.
 
○ Review investigator files for completeness and compliance with the protocol and other appropriate regulations.
 
○ Review adverse events/serious adverse events reports and comply with country specific reporting legislation, if applicable.
 
○ Prepare written reports of each visit which include but are not limited to: visit date; monitor name; site name; PI name; findings; and actions taken if any.
 
○ Provide consolation at Investigator's request.
 
 
 

## BACKGROUND / RATIONALE

Coronaviruses are a large family of viruses that cause illness ranging from the common cold to more severe diseases such as MERS and SARS-CoV. A novel coronavirus (SARS-CoV-2) was discovered in December 2019 and has resulted in millions of confirmed human infections worldwide. COVID-19, the disease brought on by the virus, produces symptoms in infected patients that are similar to the other viral respiratory diseases including fever, cough, and shortness of breath. The median incubation time is estimated to be approximately 5 days with symptoms estimated to be present within 12 days of infection. As the number of SARS-CoV-2 infections continues to increase, there is growing demand for diagnostic tests that can produce rapid, accurate and accessible results.

To help address this need, the goal of the project is to develop a low-cost, non-invasive rapid point-of-care diagnostic test for the qualitative detection of SARS-CoV-2 in respiratory specimens. Current methodology for detecting SARS-CoV-2 is a molecular-based test that utilizes RT-PCR. This is a laborious process that requires expensive equipment and reagents, special training, and can take hours until test results are available. The PHASE Diagnostics rapid test is a qualitative lateral-flow immunoassay to determine the presence of SARS-CoV-2 in respiratory samples in a single hand-held device, with a time-to-result of 15 minutes.

## PRODUCT DESCRIPTION AND INTENDED USE

The INDICAID Rapid Antigen Test Kit includes 25 individually sealed single-use Test Devices, 25 Buffer Solution Vials, and 25 sterile Nasal Swabs. A Quick Reference Instruction Sheet is provided with each test kit.

The INDICAID COVID-19 Rapid Antigen Test (INDICAID Rapid Test) is a lateral flow immunoassay (LFA) intended for the qualitative detection of nucleocapsid protein antigen from SARS-CoV-2 in direct nasal swabs from individuals suspected of COVID-19 by their healthcare provider within the first 7 days of symptom onset.

In the USA, testing is limited to laboratories certified under the Clinical Laboratory Improvement Amendments of 1988 (CLIA), 42 U.S.C. §263a, that meet the requirements to perform moderate, high, or waived complexity tests. The INDICAID Rapid Test is intended for use at the Point of Care (POC), i.e., in patient care settings operating under a CLIA Certificate of Waiver, Certificate of Compliance, or Certificate of Accreditation. The test is intended for use by medical professionals or trained personnel specifically instructed and trained in the techniques of in vitro diagnostic procedures and proper infection control procedures, and individuals similarly trained in point of care settings but who are not laboratory professionals.

Positive results are for the identification of SARS-CoV-2 nucleocapsid antigen. This antigen is generally detectable in upper respiratory samples during the acute phase of infection. Positive results indicate the presence of viral antigens, but clinical correlation with patient history and other diagnostic information is necessary to determine infection status. Positive results do not rule out bacterial infection or co-infection with other viruses. The agent detected may not be the definite cause of disease. Laboratories within the United States and its territories are required to report all positive results to the appropriate public health authorities.

Negative results should be treated as presumptive, do not rule out SARS-CoV-2 infection and should not be used as the sole basis for treatment or patient management decisions, including infection control decisions. Negative results should be considered in the context of a patient's recent exposures, history and the presence of clinical signs and symptoms consistent with COVID-19, and confirmed with a molecular assay, if necessary, for patient management.

#### PRINCIPLE OF TEST

The INDICAID Rapid Test is a chromatographic rapid test (approximately 20 minutes) that uses a sandwich immunoassay design to directly and qualitatively detect the presence or absence of SARS-CoV-2 nucleocapsid protein. The results of the test are visually interpreted.

After collecting the swab, the patient's sample is placed in the Buffer Solution Vial containing an extraction buffer. The sample is dispensed into the sample well of the test device and migrates through the test strip that contains antibodies conjugated to a chromophore (detector particle). This antibody-chromophore conjugate will bind to the nucleocapsid protein of the SARS-CoV-2 virus if present in the sample. The sample continues to flow through the test strip and is trapped by capture antibodies, which can be visually observed by the presence of the test line ("T").

#### STUDY OVERVIEW

The purpose of this study is to evaluate the clinical performance of the INDICAID Rapid Test. This will be established by determining the positive percent agreement (PPA), negative percent agreement (NPA), and overall percent agreement (OPA) between the results of the test under investigation and an EUA-approved RT-PCR test, using clinical samples collected from COVID-19 symptomatic individuals. A minimum of 30 RT-PCR SARS-CoV-2 positive and 30 negative patients are required to assess the clinical performance.

#### STUDY OBJECTIVE

The objective of this study is to assess the clinical performance of the INDICAID Rapid Test device in the hands of the intended user at the point-of-care (POC) setting.

## SITE REQUIREMENTS

Target sites include point-of-care clinic and testing settings with non-laboratory healthcare professionals located in the US.

Study sites agrees to the following:

- Strictly adhere to the testing procedures outlined in this study protocol.
- Obtain informed consent for each patient (participant) enrolled.
- Provide complete and legible data and information.
- Adhere to applicable rules of human subject protection when collect patient specimens (21 CFR Part 50 and 56.103(a)).
- Collect specimens in accordance with the collection method needed for the comparator method (RT-PCR test)

## STUDY DESIGN

### Study Duration

This study will take place across 2 testing sites for 60 days or until patient enrollment targets are met (minimum of 30 RT-PCR SARS-CoV-2 positive and 30 negative patients).

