### Sample Enrichment

In order to enrich for positive patient samples, we will be enrolling patients who have previously been tested with an FDA EUA approved Antigen Test until we obtain the required 30 positive and 30 negative specimens (as tested by the comparator RT-PCR test).

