### Study Participant Withdrawn or Excluded After Enrollment

If, after enrollment, a study participant is found to have not met an inclusion criterion, the study participant will be withdrawn from the study and any completed test results will be excluded from data analyses.

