## Statistical Analysis Plan

INDICAID COVID-19 Rapid Antigen Test	Reference Test RT-PCR			
		Infected	Not Infected	Total
	Positive	TP	FP	TP+FP
	Negative	FN	TN	FN+TN
	Total	TP+FN	FP+TN	TP+FP+FN+TN

TP = true positive

TN = true negative

FP = false positive

FN = false negative

PPA =  $TP/(TP+FN)$

NPA =  $TN/(TN+FP)$

OPA =  $(TP+TN)/\text{Total Samples}$

The following performance characteristics will be computed: PPA, NPA, OPA and accuracy. The 95% confidence interval for these performance characteristics will be computed using Wilson-Score method.

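### Does the 60-day limit let the study close short of the 30 positives and 30 negatives it requires?

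*Combined protocol and SAP*

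**What the plan says.** Three sections of the Combined protocol and SAP bear on when enrolment ends.

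- Study Duration: "This study will take place across 2 testing sites for 60 days or until patient enrollment targets are met". A parenthesis then defines the targets as a "minimum of 30 RT-PCR SARS-CoV-2 positive and 30 negative patients". Nothing says whether the earlier or the later of the two limits applies.
- Study Overview: "A minimum of 30 RT-PCR SARS-CoV-2 positive and 30 negative patients are required to assess the clinical performance".
- Sample Enrichment: patients with a prior antigen test are enrolled "until we obtain the required 30 positive and 30 negative specimens", judged by the comparator RT-PCR. No time limit is attached.

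A fourth section affects the count. Under Study Participant Withdrawn or Excluded After Enrollment, if someone is later found not to have met an inclusion criterion, "the study participant will be withdrawn from the study and any completed test results will be excluded from data analyses". The section does not mention replacement.

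On analysis, the Statistical Analysis Plan section says: "The 95% confidence interval for these performance characteristics will be computed using Wilson-Score method".

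**The concern.** The word joining the calendar limit to the target has no precedence rule. A team that closed on day 60 with, say, 18 positives could claim to have followed Study Duration while failing the Study Overview and Sample Enrichment.

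There is a second, smaller gap. If the 30 are counted before ineligible participants are removed, the analysed number could fall below 30 even though the target had been met on paper.

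Precision is at stake. The 30 per class is the only overall sample size given, and no precision goal or performance threshold stands behind it. At a given observed agreement, the number of RT-PCR positives sets the width of the interval for PPA, and the number of negatives does the same for NPA.

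**Working it through.** **1. Can the 30 per class be reproduced?** No. The documents give no expected PPA or NPA, precision target, performance goal, positive share, accrual rate or exclusion rate. The figure has to be taken as stated.

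**2. Which conduct satisfies every section?**

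| Conduct | Study Duration | Study Overview | Sample Enrichment |
|---|---|---|---|
| Close on day 60 below 30/30 | allowed on one reading | breached | breached |
| Continue past day 60 until 30/30 | allowed on one reading | met | met |
| Close before day 60 at 30/30 | allowed on one reading | met | met |

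Only enrolling to target agrees with all three sections. Study Duration also repeats the minimum in its own parenthesis, which fits reading the 60 days as an expected length.

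**3. What would a shortfall cost?** With observed proportion p, class size n and z = 1.96, the Wilson interval has

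- centre = (p + z²/2n) / (1 + z²/n)
- half-width = z √(p(1−p)/n + z²/4n²) / (1 + z²/n)

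For 27/30, z² = 3.8416 and 1 + z²/n = 1.1281. The centre is (0.9000 + 0.0640)/1.1281 = 0.8546. The half-width is 1.96 × 0.06377/1.1281 = 0.1108. The interval is 74.4% to 96.5%.

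The other rows use the same formula. Every class size below 30 is an assumption.

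| Result | Observed | 95% Wilson interval | Half-width (points) |
|---|---|---|---|
| 27/30 | 90.0% | 74.4 to 96.5 | 11.1 |
| 24/27 | 88.9% | 71.9 to 96.1 | 12.1 |
| 18/20 | 90.0% | 69.9 to 97.2 | 13.7 |
| 26/30 | 86.7% | 70.3 to 94.7 | 12.2 |
| 17/20 | 85.0% | 64.0 to 94.8 | 15.4 |
| 13/15 | 86.7% | 62.1 to 96.3 | 17.1 |

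Class size is not the only influence on width. With n fixed at 30, the half-width is 5.7 points for 30/30 (88.6 to 100) and 13.9 points for 24/30 (62.7 to 90.5). That difference of 8.2 points is larger than the 17.1 − 12.2 = 4.9 points lost by halving the positives from 30 to 15 at 86.7%.

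**4. What do exclusions cost?** At assumed exclusion rates of 2%, 5% and 10%, 60 participants would yield 1.2, 3 and 6 expected exclusions. The chance of at least one, 1 − (1 − d)^60, is 70%, 95% and over 99%. Some loss is therefore likely, but its effect is small. Moving from 26/30 to 25/29 changes the half-width from 12.2 to 12.5 points. Losing three of 30, from 27/30 to 24/27, changes it from 11.1 to 12.1 points.

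If the 30 are analysed patients, enrolment runs until the losses are made good. Using 30/(1 − d) rounded up, that takes about 31, 32 or 34 enrolled per class at the three assumed rates.

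**The case for a change.** The strongest case for a change is that the conflict sits in current text (the Revision History lists only version 1.0), that no section says what happens if day 60 comes first, and that one sentence would settle it. No other rule protects the 30. Five operators with at least three positives and three negatives each secure only 5 × 3 = 15 per class. Sites also record INDICAID results as they go, so an undefined end leaves some discretion over when to stop.

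Part of this stands. The missing precedence rule is real, one plain reading does conflict with two other sections, and the plan does not say whether the 30 are counted before or after exclusions.

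The rest is weaker.

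- The plan nowhere says that excluded participants go unreplaced; it is silent. The Study Overview ties the minimum to assessing performance. Patients whose results are dropped cannot contribute to that, so enrolling until the required number is obtained replaces them.
- Both limits that are written down, a date and a count of RT-PCR results, are defined without reference to agreement between the two tests. Neither steers PPA or NPA. Discretion informed by INDICAID results would be a departure from the plan, since no section provides for it.
- Nothing in the documents suggests that day 60 would arrive first, and the design enriches for positives.

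**Conclusion.** The concern does not hold as a defect that needs correcting. Study Duration is loosely worded, but the Study Overview and Sample Enrichment both demand 30 positives and 30 negatives, and a sponsor following the whole plan would enrol to that number and count the patients analysed. A clarifying sentence would be harmless, but it would only record what the plan already implies.

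If the calendar did bind, the loss would be in precision. At 90% agreement the half-width would go from 11.1 points with 30 positives to 13.7 with 20. At 86.7% it would go from 12.2 with 30 to 17.1 with 15. The PPA estimate and its Wilson interval would remain valid for the number observed, and the wider interval would show the shortfall to any reader. Loss through exclusions is smaller, about 0.3 points for one patient and 1.0 point for three.

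This conclusion rests on reading the sections together, on two-sided 95% Wilson intervals, and on illustrative shortfalls and exclusion rates, because the documents give no accrual, positive yield or exclusion rate. It would weaken if the sponsor treated 60 days as a hard stop that overrides the stated minimum. No section says that it does.

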### Sample Enrichment

In order to enrich for positive patient samples, we will be enrolling patients who have previously been tested with an FDA EUA approved Antigen Test until we obtain the required 30 positive and 30 negative specimens (as tested by the comparator RT-PCR test).

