#### Inclusion Criteria

- Study participant has provided verbal informed consent as required by reviewing institutional review board (IRB). The Experimental Bill of Rights will also be provided for all study participants enrolled in applicable states.
- Study participant is at least 5 years of age. Participants under 18 years old requires parental/legal care provider consent.
- Study participant reports at least 2 of the following COVID-19 symptoms:
  - Fever or chills
  - Fatigue
  - Sore throat
  - Congestion or runny nose
  - Cough
  - Headache
  - Diarrhea
  - Shortness of breath or difficulty breathing
  - Muscle or body aches
  - New loss of taste or smell
  - Nausea or vomiting
- On-set of symptoms must be within 7 days.
- Study participant has been previously tested with an FDA EUA SARS-CoV-2 Antigen test as part of the clinic site standard of care and with test results known.
- Study participant agrees to provide the following specimens for this study:
  - Three (3) clinician-collected nasal swabs (two swabs to perform sequential INDICAID Rapid Tests and a third to perform the comparator FDA EUA RT-PCR test. See below for sample collection instructions)

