#### Bias Minimization and Elimination

To minimize bias in specimen analysis by the INDICAID Rapid test, the following practices will be employed:

- Each site will be identified with a numerical ID code
- Patients eligible for the study will be screened by a separate clinic personnel not involved in collecting patient samples or performing the INDICAID Rapid Test.
- Operators collecting the patient samples and performing the INDICAID Rapid Test shall be blinded to the result of any prior rapid antigen test or comparator RT-PCR test.

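### Enrichment runs through a known prior antigen result, but the plan neither says how that result steers enrolment nor uses it in the analysis, so crude PPA may not apply to the intended-use population

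*Combined protocol and SAP*

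**What the plan says.** Sample Enrichment gives both the purpose and the means: "In order to enrich for positive patient samples, we will be enrolling patients who have previously been tested with an FDA EUA approved Antigen Test", continuing "until we obtain the required 30 positive and 30 negative specimens (as tested by the comparator RT-PCR test". The Inclusion Criteria make the prior test an entry condition, done "as part of the clinic site standard of care and with test results known". Neither section says which result is wanted, in what proportion, or whether enrolment is consecutive. No interval is set between the prior test and the study swabs.

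Bias Minimization and Elimination separates the roles: "Patients eligible for the study will be screened by a separate clinic personnel not involved in collecting patient samples", while the operators who collect samples and run the test "shall be blinded to the result of any prior rapid antigen test or comparator RT-PCR test".

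The two specimen collection and testing sections (INDICAID and comparator) list what goes on the Data Collection Form: operator, patient, collection date and the results of the two study tests. The prior antigen result is not listed.

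The Statistical Analysis Plan builds one two-by-two table of INDICAID against RT-PCR and computes PPA, NPA, OPA and accuracy. On precision it says: "The 95% confidence interval for these performance characteristics will be computed using Wilson-Score method". Nothing is split or weighted by prior result.

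The intended use is for samples "from individuals suspected of COVID-19 by their healthcare provider within the first 7 days of symptom onset", and the Study Overview speaks of "using clinical samples collected from COVID-19 symptomatic individuals". Neither sets a condition on an earlier antigen test.

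**The concern.** PPA is an average over two kinds of RT-PCR-positive patient: those the earlier antigen test detected and those it missed. Both tests look for viral antigen, so it is plausible, though the documents give no data, that INDICAID is positive more often in the first group. If enrolment raises that group's share above its natural level, crude PPA rises with no change in the device.

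The plan leaves this open. Its stated aim is more positives, and the person choosing patients knows the prior result. RT-PCR counts decide when enrolment ends, but a sample shipped to an outside laboratory cannot guide selection at the same visit. Blinding the operators protects the reading of the test, not the choice of patients. A Wilson interval reflects sampling error only and would not reveal a shift in the mix. Without the prior result in the analysis and some record of the mix screened, a reader of the final report could not tell upward, downward and no bias apart.

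**Working it through.** **The plan's own figure.** The documents give 30 RT-PCR positives and 30 negatives as minima, with no target PPA and no assumed rates. There is nothing to reproduce beyond n = 30. Every rate below is an assumption.

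**Notation, among RT-PCR positives.**
- s: natural share who are prior-antigen positive (the prior test's sensitivity). Assumed 0.80.
- k: how many times more readily a prior-positive is enrolled than a prior-negative.
- f: enrolled share of prior-positives, f = ks / (ks + 1 − s).
- a, b: INDICAID positivity in prior-positives and prior-negatives; the gap is a − b.

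**Formula.** Crude PPA = fa + (1 − f)b. Unselected PPA = sa + (1 − s)b. Subtracting, bias = (f − s)(a − b). This is zero if k = 1 or a = b, and negative if k < 1 with a > b.

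**Shift in share at s = 0.80.**
- k = 0.5: f = 0.40/0.60 = 0.667, f − s = −0.133
- k = 2: f = 1.60/1.80 = 0.889, f − s = +0.089
- k = 5: f = 4.00/4.20 = 0.952, f − s = +0.152

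**Bias in PPA, percentage points.**

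| Gap a − b | k = 2 | k = 5 |
|---|---|---|
| 0 | 0 | 0 |
| 10 | +0.9 | +1.5 |
| 25 | +2.2 | +3.8 |
| 50 | +4.4 | +7.6 |
| 75 | +6.7 | +11.4 |

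In the other direction, k = 0.5 with a 75-point gap gives −0.133 × 75 = −10.0 points.

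**Dependence on s.** At a 75-point gap and k = 2, s = 0.70 gives (0.824 − 0.70) × 75 = +9.3 points and s = 0.90 gives (0.947 − 0.90) × 75 = +3.6. At k = 5 these become (0.921 − 0.70) × 75 = +16.6 and (0.978 − 0.90) × 75 = +5.9.

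**Against sampling error at n = 30.** The 95% Wilson interval for 24/30 (80.0%) is 62.7% to 90.5%. The table gives how often the nominal 95% interval contains an unselected PPA of 80.0%, by exact binomial sum. All three (a, b) pairs give 0.8a + 0.2b = 0.80.

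| a, b | Gap | k = 1 | k = 2 | k = 5 |
|---|---|---|---|---|
| 0.85, 0.60 | 25 | 96.4% | 96.8% | 96.1% |
| 0.90, 0.40 | 50 | 96.4% | 95.5% | 90.0% |
| 0.95, 0.20 | 75 | 96.4% | 92.2% | 74.1% |

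Of the over-selection cases shown, only a 75-point gap combined with five-fold over-selection costs a great deal of coverage.

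**Size of the informative stratum.** Expected prior-negatives among 30 RT-PCR positives are 30(1 − f): 6.0 at k = 1, 3.3 at k = 2 and 1.4 at k = 5. The chance of none, f^30, is 0.1%, 3% and 23%. An observed 1/3 has a Wilson interval of 6.1% to 79.2%.

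**The case against.** **Selection by result is inferred, not written.** A reader might infer that the sites will pick prior-positives and that the reported PPA will therefore be inflated. The documents do not support that. Patients with either prior result qualify, and no section prefers one. A standard-of-care antigen test may also mark clinical suspicion, which could raise the yield of positives without any choice by result and bring the sample nearer to the intended use. This objection stands against any claim that bias will occur. It does not answer the point that the plan leaves the rule unstated and the result unanalysed.

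**Screeners who know the result are not a flaw in themselves.** They must know that a result exists to apply the inclusion criterion, and keeping them apart from blinded operators is a sensible guard against reading bias. This stands.

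**The large figures need extreme assumptions.** This also stands. With a 25-point gap, coverage remains at 96% to 97% even at five-fold over-selection.

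**The study objective is use by the intended operators at the point of care, and the enrichment is openly disclosed.** Both are true. But the Study Overview sets out to establish clinical performance in symptomatic individuals, and PPA is a headline measure of it. Disclosing that enrichment occurred does not tell a reader how it altered the mix.

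**Splitting by prior result adds little precision, and a tally of eligible but unenrolled patients would be nearly empty,** because consent and swab provision are themselves eligibility criteria. Both parts are correct and shape the fix.

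**Conclusion.** The concern holds in conditional form. The plan enriches through a known prior antigen result, does not say how that result governs enrolment, and reports crude agreement that ignores it. Crude PPA is too high for the intended-use population only if prior-positives are over-represented among RT-PCR positives and the two antigen tests tend to agree. The documents establish neither condition.

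Under an assumed 80% prior-test sensitivity and gaps of 0 to 75 points, the bias runs from 0 to +6.7 points at two-fold and from 0 to +11.4 points at five-fold over-selection; it reverses if prior-negatives are over-selected. Up to two-fold it is within ordinary imprecision at 30 positives. A reader might take the 74% coverage as typical; it is the result of the largest gap and the strongest over-selection together.

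This should be fixed because the repair is cheap and the screening mix is hard to reconstruct later. Confidence is medium, since the sign and size rest on assumptions. The prior result may exist in clinic records or on forms not shown, so the finding is that the plan does not use it, not that it is unobtainable. The enrichment itself can stay.

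**What to change.** 1. In Sample Enrichment, state whether and how the prior antigen result is used to select patients, including a plain statement if it is not used.
2. Have the screener, not the blinded operator, record the prior antigen result and its date for each enrolled patient, on a form the operator does not see. Keep a de-identified count, by prior result, of symptomatic, previously tested patients screened. A count at screening avoids the near-empty category of eligible but unenrolled patients.
3. In the Statistical Analysis Plan, add a table of INDICAID by RT-PCR results split by prior antigen result, with PPA, NPA, Wilson intervals and counts. Mark a stratum as not estimable where it is empty.
4. Describe crude PPA and NPA as applying to a previously antigen-tested sample, and to an antigen-enriched sample if the prior result was used in selection. Do not present them as direct estimates for the intended-use population.

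**Cost.** A form field with its date, a simple count and one extra table, with no added patients and operator blinding intact. The claim becomes narrower. With about 1 to 6 prior-negatives expected among 30 RT-PCR positives under the assumptions above, the table will show how far PPA rests on prior-positives but will not estimate the prior-negative stratum precisely.
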